## **12. INFORMED CONSENT**

Once a potential study participant expresses interest in our study and meets preliminary eligibility requirements, as determined by the brief phone screen, a written consent form will be sent to the subject either electronically or via mail. Consenting procedures will be HIPAA compliant. Upon receipt of written consent, recruitment contact will further explain by phone the details of the consent. The subject recruiter will present to study participants the objectives, procedures and a clear statement explaining risks and benefits involved in the study. Questions will be asked and elicited in order to ascertain that participants comprehend the study procedures as well as potential risks involved, prior to consenting to the study. All study related questions from study participants that a research staff is unable to address will be referred to one of the principal investigator, Drs. [name] and [name], or other co-investigators. Once a participant signed the consent form, the participant is considered enrolled in the study.

Participants will sign a separate consent form if they are interested in the future genetic study. The same consenting procedure described above will be followed.

## **13. ALTERNATIVES TO STUDY PARTICIPATION**

This is not a therapeutic study, and there are no alternatives.

## **14. POTENTIAL RISKS**

**Risks of Psychological and Cognitive Assessments.** The main risks are that clinical interviews, cognitive testing and self-report questionnaires are time consuming. Material elicited during interviews may be upsetting to some study participants. Others may find cognitive tasks to be challenging or frustrating. These assessments, however, rarely pose psychological risks for study participants. It is our experience that REC ED subjects and CW will be willing to cooperate with such studies. These studies have not been psychologically traumatic to REC ED patients in the past. It should be noted that REC ED subjects are often motivated by altruistic feelings and are usually cooperative with studies that serve to develop a better understanding of EDs. We do not feel that these studies pose any significant psychological risk for the patients.

**Risks of Venipuncture and Blood Sampling.** There is minor discomfort and potentially significant psychological distress associated with venipuncture, if the procedure is not well-handled. There is a rare risk associated with the chance of infection or light-headedness or fainting due to blood withdrawal (less than 1 out of 100 people) and a more common risk (10 to 25 out of 100 people) of slight pain, bruising, bleeding or soreness associated with taking blood from a vein.

**Risks of Catheterization.** Insertion of a catheter for intravenous injection of the PET radiopharmaceutical is rarely associated with the chance of infection (less than 1 out of 100 people), but more commonly associated with slight pain or bruising at the puncture site (10-25 out of 100 people).

**Risks of MRI.** According to the FDA, there is currently no evidence that MRI with approved scanners of up to 4 Tesla signal strength are associated with adverse effects. However, there are three major sources of potential risks. First, the subject may experience discomfort being in the confined and sometimes noisy environment of the scanner. Second, the strong magnetic field will affect electronic, magnetic and metal devices that subjects may carry with them or that have been implanted in their bodies. Third, if unprotected, hearing loss can occur with prolonged exposure to the noise generated during MRI imaging. In addition, subjects may temporarily experience dizziness and/or nausea if the individual moves rapidly through the magnetic field. There is also the potential for RF-induced local heating and for mild electric stimulation due to induced currents from rapidly switching gradients.

**Risks of administering tracer dose of [C]DASB and [C]raclopride.** Mass doses of radiotracers used in these studies are negligible. For these compounds, with affinities in the pico- to nano-molar range, the receptor occupancy is negligible, and we have not observed any pharmacological effects. However, as with any drug, the possibility of idiosyncratic reaction exists as discussed in the consent forms.

**Risk of administering oral AMPH.** The major somatic side effects of AMPH administration are cardiovascular (hypertension, palpitations, tachycardia, bradycardia, orthostasis, syncope). General effects such as sweating, feeling warm or cold, chest tightness, nausea, diarrhea, vomiting, muscle and abdominal cramping, blurred vision, and headaches, have been reported. There is a rare risk of permanent neurologic damage and death as a result of cardiac arrest or stroke. One of the largest cohort (n=81 schizophrenic and n=7 control subjects) of published safety data for 0.5 mg/kg oral AMPH is a report by Angrsit et al. In this report, the greatest changes from baseline were observed over the first hour, and absolute readings peaked at the second hour, at which point mean BP indices in subjects who received AMPH were 31 mm Hg greater for SBP (systolic blood pressure), 11 mm Hg for DBP (diastolic blood pressure), and 18 mm Hg for MAP (mean arterial pressure). They also observed a mild but significant increase in heart rate (+ 10 beats per minute from baseline) after 3 hours in the healthy controls but not in subjects with schizophrenia. Several other groups have successfully used oral AMPH in the dose range of 0.43-0.5 mg/Kg in PET imaging studies, but they have not reported any adverse effects that required medical intervention. In addition, we have not experienced any adverse effects in our pilot study.

**Risks of Radiation Exposure:** Participation in the PET imaging procedures involves exposure to small amounts of radiation. The EDE per single injection is 0.39 rems for [C]DASB and 0.25 rems for [C]raclopride. If the participants undergoes the maximum of 3 PET transmission scans, two [C]raclopride scans (10 mCi) and one [C]DASB scan (15 mCi), the combined Effective Dose Equivalent (EDE) radiation exposure will be equivalent to a whole body dose of 1.23 rem (12.3mSv) (24.64% of the annual whole body radiation exposure (5 rems) permitted to radiation workers by federal guidelines). This amount is approximately 7 times more than they would receive from the average person's annual background radiation exposure, which is approximately 160 mrem (1.6 mSv). This radiation dose is not expected to produce any harmful effects, although there is no known minimum level of radiation exposure considered to be totally free of the risk of causing genetic defects or cancer. The risk associated with the amount of radiation exposure participants received in this study is considered low and comparable to everyday risks and similar to that from many commonly performed diagnostic Nuclear Medicine Procedures. If participants are especially concerned with radiation exposure or have had a lot of x-rays already, we advise that they should discuss their concern with their doctor.

No PET studies will be performed on nursing, pregnant, or potentially pregnant women, as confirmed by serum pregnancy testing and a urine test. Adverse effects of the radiopharmaceuticals in the study have not been reported. However, the possibility exists for a rare reaction to any of the substances or procedures to which the subject is exposed. Insertion of catheters for intravenous injection of the PET radiopharmaceutical may be associated with slight pain or bruising at the puncture site.

**Risk of Breach of Confidentiality.** Breaches in confidentiality could impact future insurability, employability, or reproduction plans, or have a negative impact on family relationships, and/or result in paternity suits or stigmatization.

**Risk of Alcohol Exposure:** The production of the [C]raclopride compound contains up to 10% alcohol. This would amount to a total injected alcohol amount of 2mL of ethanol. Two mL distributed over 5000 mL whole blood or 2500 mL plasma would represent  $2/5000 = 0.4 \times 10^{-3}$  (Blood alcohol Concentration BAC 0.0004) or  $2/2500 = 0.8 \times 10^{-3}$  (BAC 0.0008) as maximum amount.

**Risks of psychological assessments:** The main risks are that clinical interviews, cognitive testing and self-report questionnaires are time consuming. Material elicited during interviews may be upsetting to some study participants. Others may find cognitive tasks to be challenging or frustrating. These assessments, however, rarely pose psychological risks for study participants.

**MRI:** The subject may experience discomfort being in the confined environment of the scanner.

**Exposure to a high magnetic field.** The only known hazard associated with exposure to a static high magnetic field is that the magnet exerts a strong force on ferromagnetic objects. For this reason, ferromagnetic objects are excluded from the vicinity of the magnet so that they will not become projectiles. In addition, each subject undergoes a standard screening procedure to determine whether they have any implanted materials that may pose a risk. If there is any doubt about the nature of any implanted material, the subject will not be scanned. Conventional MRI uses 1.5 Tesla (T) magnets. At the Keck Center for Functional MRI, the research systems for human use have field strengths of 3T. Imaging at these field strengths is not considered a significant risk according to FDA guidelines.

**Heating from radiofrequency (RF) pulses.** The RF pulses that are used for creating the MR signal deposit some energy in the body in the form of heat, but no ionizing radiation is used with MRI. For the same pulse

sequence, the RF power deposited is higher at higher magnetic field strengths. However, the pulse sequences we will use at 3T has relatively low power depositions. In the future pulse sequences with higher RF power depositions may be developed, but we will insure that the power deposited is always below the FDA guidelines.

**Peripheral nerve stimulation from rapidly switched magnetic fields (dB/dt).** Magnetic field gradients are switched on and off during imaging to encode the spatial distribution of the MR signal. Gradient switching rate depends on the gradient coil used, but does not depend on field strength. For this reason, the gradient switching rates will be similar to those for the 1.5 T scanners we have used in the past, and these rates will not exceed FDA recommendations. The FDA guideline states that a significant risk is involved only when “dB/dt sufficient to produce severe discomfort or painful stimulation” is used. All of the MRI studies performed in the past at 3T systems at UCSD are well below this threshold.

**Acoustic noise.** Acoustic noise is always an unwanted side effect of MR imaging. As currents are pulsed through the gradient coils within the magnetic field, the system acts like a loudspeaker, making a repetitive tapping sound. At the higher field strengths (3T) the acoustic noise is increased. In all our studies subjects will wear ear plugs to reduce the noise to a comfortable, safe level. The FDA guideline for a significant risk due to acoustic noise is “peak acoustic noise over 140 dB”, and we will insure that the acoustic levels remain well below this value.

**Acquisition of Eye Blink Rate.** The main risks associated with acquisition of eye blink data are associated with time consumption. Participants may become bored or irritated having to sit still and hold a fixation on a computer screen for 5 minutes. However, acquisition of this data should cause minimal risk to the research participant.

## 15. RISK MANAGEMENT PROCEDURES AND ADEQUACY OF RESOURCES

It is our experience that ED subjects and CW will be willing to cooperate with such studies. These studies have not been psychologically traumatic to ED patients in the past. It should be noted that ED subjects are often motivated by altruistic feelings and are usually cooperative with studies that serve to develop a better understanding understanding of EDs. We do not feel that these studies pose any significant psychological risk for the patients.

**Risks of Psychological and Cognitive Assessments.** While most study participants will find the clinical interviewing process to be a positive experience, some may become anxious or tearful because of the personal nature of the questions. Clinical interviewers will exercise caution and sensitivity and terminate the interview as necessary in order to protect the emotional well-being of the study participant. Similarly, study participants who experience frustration during cognitive assessments will be reassured that they are there to do their best and that it does not matter how well they score. They will be encouraged to continue but allowed to stop if continued distress is experienced. If the subject does not want to talk about any of her feelings during the study, she does not have to so, and she can tell the interviewer she does not want to talk about her feelings.

**Risks of Venipuncture and Blood Sampling.** We have a firm policy to only attempt venipuncture a maximum of twice on one occasion. In addition, we allow adequate time for the procedure, as necessitated by the individual subject. Very rarely will a subject be so anxious about venipuncture that these studies are not feasible. The taking of a blood sample may cause some discomfort. The CTRI nurse and the study staff will monitor the subjects’ condition closely to minimize any discomfort.

**MRI Related Risks.** Typically, 3 Tesla scanners have been measured to produce noise between 122-131 db. The potential risk of hearing loss associated with the noise generated during MRI is eliminated by using ear plugs (rated to reduce noise by 32 dB) and through the use of headphones (rated to reduce noise 30 dB).

Subjects will be strongly encouraged to move slowly when entering or exiting the magnetic field. The scanner bed has been designed to slowly move the subject so as to minimize the possibility of vertigo. RF-induced local heating is unlikely due to the software requirement that subject's weight is accurately recorded and used in determining the appropriate changes in gradients. Subjects are warned of the possibility of mild electric stimulation and are monitored throughout the session. Exclusions will be made for the following: cardiac pacemaker, metal fragments in eyes/skin/body (shrapnel), history of being a metal worker/welder, history of eye surgery/eyes washed out because of metal, aortic aneurysm clips, prosthesis, by-pass surgery/coronary artery clips, hearing aid, heart valve replacement, subjects with an IUD (birth control device), a shunt (ventricular or spinal), electrodes, metal plates/pins/screws/wires, or neuro/bio-stimulators (TENS unit), vision problems uncorrectable with lenses, claustrophobia, inability to lie still on one's back for approximately 30 minutes, prior neurosurgery, older tattoos with metal dyes, unwillingness to remove nose, ear, tongue or face jewelry, braces or permanent dental retainers, and women with a positive pregnancy test or currently lactating.

In addition, computers and the interfacing devices will be checked regularly for proper and safe operation. Similarly, study participants will be asked questions pertaining to fear of closed spaces during the screening stage. However, should the participant become claustrophobic during the study or for any reason be unable to endure remaining in the scanner, the study will be terminated and the participant will be removed from the scanner. In addition, a pregnancy test will be performed within 24 hours of the study. No studies will be performed on pregnant or potentially pregnant women. If there is a possibility of metal being present in the participant's body, the participant will be asked to undergo an x-ray study to rule out the presence of metal. The participant will be required to sign an additional consent form to undergo the x-ray study.

In order to minimize the risk of fear of closed spaces while in the MR scanner, patients will be extensively interviewed and informed about the nature of the task. If, at any point in during the scanning, the subject expresses increasing discomfort, the PI will immediately intervene and terminate the scanning procedure

**Exposure to high magnetic fields:** All subjects will be screened twice before they will be allowed to enter the MRI facilities. Any non-removable magnetic material will automatically exclude subjects. All staff is regularly trained in MRI safety procedures by the PI.

**Heating from radiofrequency (RF) pulses:** The MRI pulse sequences that will be used are discussed prior to usage by the MR physicists and the director of the Center for Magnetic Resonance Imaging (CMR) with respect to potential heating effects. The physicists at the CMR regularly test pulse sequences on phantom objects for heating effects.

**Acoustic noise:** Subjects will be instructed to wear earplugs or headsets that reduce the noise by about 20-40 dB. Subjects will be instructed to indicate if the noise is a source of physical or psychological discomfort. If this were to occur the experiment will be terminated immediately.

**PET and Radiation related issues** The use of [C] radioligands in this research proposal is considered to be generally safe and effective as approved by the University of California, San Diego Radioactive Drug Research Committee in accordance with Food and Drug Association regulation 21 CFR 361.1. No PET studies will be performed on pregnant or potentially pregnant women, as confirmed by pregnancy testing performed within 24 hours prior to each PET scanning session. The total Occupational Dose Limit / EDE for adults, as regulated by the US Nuclear Regulatory Commission is 5.0 rem per year. Thus, for the three studies the EDE is about 24.64% of the radiation dose (5 rem) permitted on an annual basis to radiation workers by federal regulations (21 Code of Federal Regulations (CFR) 361.1. If an X-ray study is required to rule out the presence of metallic fragments, the maximum radiation dose to the involved body area will be 0.3 rems (a unit of radiation dosage), with minimum exposure of the other areas of the body. In order to restrict the yearly cumulative exposure to

radiation as outlined in FDA 21.361.1, all subjects exposed to radiation in the work place are excluded, as well as subjects exposed to nuclear medicine procedures during the previous year, including research protocols. In case of idiosyncratic reactions to the radiotracers, a physician is present at each experiment and will be available at all times during the study and an emergency cart will be in close proximity.

**Risk of Alcohol Exposure:** The radiotracer that is injected will contain a very small amount of alcohol that is 1/1000 of what is allowed for driving a car in most states. This amount is minimal (Blood alcohol Concentration BAC 0.0004). The common legal limit for driving is a BAC of 0.8. In most cases the injected dose will be below. We do not expect that the subject will even recognize any effects from this amount of alcohol; however, we discourage subjects with a history of alcohol dependence from participating in order to avoid the risk of relapse.

**Participant Monitoring on AMPH:** Subjects with a history of hypertension or any heart disease will be excluded. Only subjects who are normotensive ( $100/70 > BP < 120/80$ ) and have a HR above 55 bpm at screening, on the day of study before the 1st [ $^{11}C$ ]raclopride scan, as well as when measured 15 minutes after the 1st [ $^{11}C$ ]raclopride scan when subject will lay supine for 5 minutes in a quiet room and have BP and HR measured, and then stand for 1 minute when HR and BP will be repeated, will receive amphetamine. As amphetamine cross-reacts with street drugs such as cocaine, a rapid drug screen will be performed on the day of the scan. The dextroamphetamine will be administered to the subject by a physician familiar with the protocol (study physician, [name]). A study physician will be available to monitor the subject until discharge. In order to monitor possible side effects of amphetamine including cardiovascular (hypertension, palpitations, tachycardia, bradycardia, orthostasis, syncope) as well as general effects such as sweating, feeling warm or cold, chest tightness, nausea, diarrhea, vomiting muscle and abdominal cramping, blurred vision and headaches, blood pressure and heart rate will be recorded every two minutes for the first 15 minutes after amphetamine administration, then every five minutes for 30 minutes, then every 15 minutes thereafter (up to at least 180 min) and then hourly until discharge. In addition, a participant will be asked to fill out an adverse event questionnaire after amphetamine ingestion in the following intervals: 10 min, 20 min, 30 min, 45 min, 60 min, 90 min, 120 min, 150 min and 180 min. If the patient has a SBP  $> 190$  or DBP  $> 130$  for greater than 5 minutes after ingestion of AMPH, then treatment with oral labetalol (200-400 mg) will be initiated. Sublingual nitroglycerin (150-600 mcg) will be administered if the patient complains of chest pain. All changes from a laying to a sitting, laying to a standing, or sitting to a standing position of the participants will be assisted by the staff on site. Participants will be requested to drink at least 1.5 liter of water between standardized breakfast and end of the 2nd scan. If the patient has psychomotor activation or behavioral symptoms suggestive of a hypomanic state, they will be treated with oral lorazepam 2 mg. If symptoms of nausea, diarrhea, muscle and abdominal cramping, or headaches occur and are persisting and becoming intolerable for the participant, we will provide respective medication (including antiemetic medication, spasmolytics and pain medication) based on the individual clinical severity and assessed by the PI and study physician, [name]. All these medications will be stored at the UCSD NeuroPET center for emergency management. Following emergency treatment with these medications, the appropriate routine medical care will be initiated and provided. If any of the above side effects persist for more than 1 hour, despite the respective medication administered as outlined below, or intensify, the participant will be sent to the nearest Emergency Department. After a syncopal event the participant will be sent to the nearest Emergency Department immediately. Following the scans, the subject will receive: a) physical exam; b) vital signs measurement; c) mental status exam and d) EKG

**Transfer Criteria:** The subject will be transferred from the UCSD PET center to the UCSD Eating Disorder Treatment and Research Center once they meet the following criteria upon evaluation by a study physician: a blood pressure of less than 150/90 mm Hg; a heart rate of less than 110 BPM; no behavioral abnormalities.

**Discharge Criteria:** After a minimum of 6 hours of observation following drug ingestion, the subject will be medically discharged from the UCSD Eating Disorder Treatment and Research Center only if they meet the following criteria upon evaluation by a study physician: a) a blood pressure (BP) of less than 20 mm Hg above

their baseline reading for systolic and diastolic BP or less than 150/90 (whichever reading is lower); b) a heart rate of less than 20 BPM above their baseline or 100 (whichever reading is lower); c) no reported subjective effects from the AMPH; d) no adverse events to the AMPH; e) a normal physical exam; f) a normal mental status exam. Most of the REC AN and BN will travel to San Diego for this study. We will establish a policy that they are required to stay the night after the study and will be discharged to travel home the next day. For the subjects that live in San Diego, we will ask a relative to drive them home after being discharged from the study.

**Confidentiality.** To minimize possible risk of breach of confidentiality, each study participant will be assigned, upon entry into the study, a numeric code which will be used as the identifier for subsequent research related activities. All information collected, including self-report questionnaires, psychological assessments, and imaging data are identified solely by these numbers without any personal identifiers. Only strictly anonymous data will be entered into the database and used for statistical analysis. Access to the numbering system will be limited to the principal investigators, Drs. [name] and [name], and their research staff involved in the study. Research files will be kept in locked quarters and made available only to qualified personnel for research purposes. No verbal or written information concerning a subject will be released to anyone without expressed written consent by the subject.

If blood samples are obtained for genetic sampling, all samples will be labeled by code numbers only and identifiable only by the PIs of this protocol, as knowledge of genetic research data could potentially impact future insurability, employability, or reproduction plans; or have a negative impact on family relationships; and/or result in shame or embarrassment.

**Others.** Unanticipated findings of potential medical significance uncovered during the course of the study, including a positive pregnancy test or an abnormal MRI, will be reported to the PIs. The study participant will be informed of the test result and then referred to her physician. If the participant does not have a regular physician, an appropriate referral will be made. If the participant does not have a regular physician, an appropriate referral will be made. In the unlikely event that a subject is injured during the study, she will receive care from the University of California as needed to treat the injury.

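### The blood-pressure criterion for giving amphetamine has its first inequality sign reversed, so as printed it sets two upper limits and no lower limit

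*Combined protocol and SAP*

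**What the plan says.** Section 15, under Participant Monitoring on AMPH, decides who receives the drug. It opens with a history-based exclusion: "Subjects with a history of hypertension or any heart disease will be excluded". It then sets the pre-dose condition. "Only subjects who are normotensive", defined in brackets as "100/70 > BP < 120/80", and who also "have a HR above 55 bpm at screening" may be dosed. The condition is checked at screening, on the study day before the first raclopride scan, and again 15 minutes after that scan.

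Other sections touch on blood pressure without restating this range:

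- Section 9 (Study-Day Session Procedures and PET scan protocol) gives only the recording schedule.
- Section 10 (inclusion, exclusion and control criteria) contains no blood-pressure limit.
- Section 14 (Risk of administering oral AMPH) reports the expected change from a published cohort: "mean BP indices in subjects who received AMPH were 31 mm Hg greater for SBP", with a diastolic rise of 11 mm Hg.
- Section 15 has a post-dose treatment trigger (systolic above 190 or diastolic above 130 for more than 5 minutes). Its Transfer Criteria have a post-dose ceiling, "a blood pressure of less than 150/90 mm Hg", and the Discharge Criteria also set ceilings.

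**The concern.** The bracket prints two limits in ascending order as the definition of normotensive, so it should describe an interval. The direction of the first sign prevents that. With the sign pointing that way, 100/70 is a ceiling rather than a floor. It is also the tighter of the two ceilings, so the second limit never operates.

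This is not background text. It is the only statement of the pre-dose pressure range for a 0.5 mg/kg oral stimulant challenge, and the only place a lower limit could come from. Anyone auditing doses against the protocol as written would record as violations the women the criterion is meant to admit. The substantive loss is the floor: orthostasis and syncope are among the listed amphetamine effects in sections 14 and 15, and the companion heart-rate criterion is itself a lower limit.

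**Working it through.** No sample-size, power or alpha figure is involved. The check is a logical evaluation of the bracket, using these inputs from section 15: limits 100/70 and 120/80, the two signs as printed, and the label normotensive. Each limit is applied to systolic (S) and diastolic (D) pressure in mm Hg, and both components are assumed to have to pass.

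**As printed**

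- The first sign gives S < 100 and D < 70.
- The second sign gives S < 120 and D < 80, which is already implied by the first.
- The rule is therefore S < 100 and D < 70. The highest whole-number reading admitted is 99/69, and there is no lowest.

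**With the first sign turned round**

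- 100 < S < 120 and 70 < D < 80. In whole numbers, S runs from 101 to 119 and D from 71 to 79.

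**Difference in the operative ceiling:** 120 − 100 = 20 mm Hg systolic and 80 − 70 = 10 mm Hg diastolic.

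| Reading | As printed | Sign corrected |
|---|---|---|
| 85/55 | admitted | refused |
| 95/65 | admitted | refused |
| 99/69 | admitted | refused |
| 105/72 | refused | admitted |
| 110/75 | refused | admitted |
| 119/79 | refused | admitted |
| 125/85 | refused | refused |

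**Overlap.** The printed rule needs S < 100 and the corrected rule needs S > 100, so no reading satisfies both. Enumeration over whole numbers (S from 60 to 160, D from 30 to 110, S > D) confirms this:

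- Corrected rule: 19 × 9 = 171 readings.
- Printed rule: S from 60 to 99 and D from 30 to 69 gives 40 × 40 = 1,600 pairs. Removing the 55 with S ≤ D leaves 1,545.
- Readings in common: 0.

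These are counts of possible readings. They say nothing about how many women would fall on either side.

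**Can another section repair it?** No. The section 9 schedule has no thresholds, section 10 has no pressure limit, and the hypertension exclusion is by history. The 190/130 trigger and the 150/90 limit apply after dosing and are ceilings.

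**The case against.** The strongest reply is that this is a slip any clinician corrects on sight. The bracket explains the word normotensive, its two limits are in ascending order, and under the literal reading the second has no purpose. Section 15 has a physician familiar with the protocol give the drug, and it is hard to imagine that physician refusing 110/75 and dosing only women below 100/70. That stands, and it keeps the point small. It does not make the criterion correct as written.

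A second reply is that the sign may have been misread when the PDF was converted. That cannot be excluded. Nothing nearby points to it, though: the other inequality signs in the same paragraph (below 120/80, above 190, above 130) read sensibly. The fix begins with a check of the source for this reason.

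A third reply is that a missing floor matters little. The only quantified pressure effect in the protocol is a rise, and section 15 does not say what the floor is for. Low-pressure events are also covered in part by assisted changes of position, at least 1.5 litres of water, frequent pressure recording and physician availability until discharge. This also stands.

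Stronger readings are tempting, and the documents do not support them:

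- **Hypertensive women could be dosed.** A reader might infer this from a faulty safety limit. The printed error lowers the ceiling, so 125/85 is refused either way.
- **Hypotensive women are being dosed, or most eligible women are being turned away.** Nothing shows that the literal rule is applied. The Progress Report counts 47 raclopride scans but does not say how many women went on to a post-amphetamine scan, so it cannot settle the matter.
- **The criterion is also defective because it gives no rule for readings with one component inside and one outside the range, or for the standing measurement.** That is a request for more detail. It would arise equally with the sign correct, and it is not part of this point.

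**Conclusion.** The point holds as a minor correction to one safety criterion. The printed bracket means a pressure below 100/70 with no lower limit, excludes every reading between its own two bounds, and contradicts the term it defines. No other section corrects it.

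Its practical size is one missing low-pressure floor, partly covered by the monitoring already in place. There is no effect on sample size, power or any analysis.

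The conclusion rests on two assumptions. The first is that the sign in the source document is as it appears in the text reviewed. The second is that both components must satisfy a limit; the ceiling shift, the zero overlap and the statement that no hypertensive reading is admitted use it. The contrast between 95/65 and 110/75 does not depend on it, because both components of each reading fall on the same side.

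**What to change.** Check the first inequality sign in section 15 (Participant Monitoring on AMPH) against the source document. If it is printed as it appears here, replace the bracket with 100/70 < BP < 120/80, leaving the heart-rate criterion and the three time points as they are. The cost is one character in a protocol correction. Nothing in the design, sample size or analysis plan changes.
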